8.1.10.3 Visit 16 (Assessment visit end of treatment with Concizumab) - Extension part

Visit 16 is to be scheduled on trial day 533 (76 weeks) with a visit window of ± 7 days.

Visit 16 should be scheduled to be conducted at the last day of treatment with concizumab.

Treatment with concizumab must take place after the blood sampling at this visit.

Patients will be asked to complete the PRO questionnaires before any other trial related activities are performed according to section [8.6.1](#);

Protocol
 Trial ID:NN7415-4255
 UTN:U1111-1179-3872
 EudraCT no.:2016-000614-29

~~CONFIDENTIAL~~

Date: 18 December 2017
 Version: 3
 Status: Final
 Page: 51 of 124

Novo Nordisk

- Hemo-TEM
- SF-36v2
- SDS
- TSQM
- H-DAT
- SIAQ-ISRQ

Assessments are to be performed according to [Table 2–1](#) and the assessment results from concomitant medication, vital signs and details of adverse events (AE) must be entered into the eCRF.

Investigator is to perform compliance check of treatment and reporting of bleeding episodes through reviewing collected data from the eDiary.

In the period from visit 16 to visit 17 the patient can be treated with turoctocog alfa (rFVIII) at the discretion of the investigator. Treatment can either be prophylactically and/or treatment of eventual bleeding episodes. Only turoctocog alfa will be provided by Novo Nordisk.

If necessary, a dispensing call must be performed in the IWRS. At the visit the patient will be provided with rFVIII (turoctocog alfa) and injection kits to be able to conduct home treatment until final visit.

The patient will be asked to return all used, partly used and unused concizumab cartridges and turoctocog alfa (FVIII) during the trial as instructed by the investigator. NovoPen 4 must be returned. Drug accountability must be performed at all visits for concizumab and rFVIII (turoctocog alfa) including injection kits, if applicable. Unused sodium chloride syringes should be returned to site at every visit and new sodium chloride syringes should be dispensed to the patient.

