17.6.2 Supportive secondary safety endpoints

- Number of treatment-emergent adverse events (TEAEs) during at least 24 weeks from treatment onset
- Number of TEAEs during 76 weeks from treatment onset.
- Occurrence of anti-concizumab antibodies during at least 24 weeks from treatment onset.
- Occurrence of anti-concizumab antibodies during 76 weeks from treatment onset.
- Change from baseline of fibrinogen during 24 weeks from treatment onset.
- Change from baseline of fibrinogen during 76 weeks from treatment onset.

Protocol
 Trial ID:NN7415-4255
 UTN:U1111-1179-3872
 EudraCT no.:2016-000614-29

~~CONFIDENTIAL~~

Date: 18 December 2017
 Version: 3
 Status: Final
 Page: 103 of 124

Novo Nordisk

- Change from baseline of D-dimer during 24 weeks from treatment onset.
- Change from baseline of D-dimer during 76 weeks from treatment onset
- Change from baseline of prothrombin fragment 1 + 2 (F1 + 2) during 24 weeks from treatment onset.
- Change from baseline of F1 + 2 during 76 weeks from treatment onset.
- Change from baseline of prothrombin time (PT) during 24 weeks from treatment onset.
- Change from baseline of PT during 76 weeks from treatment onset.
- Change from baseline of activated partial thromboplastin time (APTT) during 24 weeks from treatment onset.
- Change from baseline of APTT during 76 weeks from treatment onset.
- Change from baseline of antithrombin (AT) during 24 weeks from treatment onset.
- Change from baseline of AT 76 weeks from treatment onset.

Adverse Events will be coded using the most recent version of Medical Dictionary for Regulatory Activities (MedDRA) coding.

A Treatment Emergent Adverse Event (TEAE) is defined as an event that has onset from the first exposure to treatment until the last visit in the trial. Treatment-emergent adverse event endpoints will be summarised by system organ class, preferred term, seriousness, severity and relation to trial product. All Adverse events will further be listed.

Frequency of binding anti-concizumab antibodies will be listed and summarised by time frame according to the two endpoint definitions.

All laboratory safety endpoints will be plotted by time, both as absolute values and change from baseline. Laboratory safety endpoints will further be summarised and listed.

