4.2.2 Secondary endpoints

4.2.2.1 Supportive secondary endpoints

- **Supportive secondary efficacy endpoints**
- The number of bleeding episodes during 76 weeks from treatment onset
- The number of spontaneous bleeding episodes during at least 24 weeks from treatment onset
- The number of spontaneous bleeding episodes during 76 weeks from treatment onset
- **Supportive secondary safety endpoints**
- Number of treatment-emergent adverse events (TEAEs) during at least 24 weeks from treatment onset
- Number of TEAEs during 76 weeks from treatment onset
- Occurrence of anti-concizumab antibodies during at least 24 weeks from treatment onset
- Occurrence of anti-concizumab antibodies during 76 weeks from treatment onset
-
- Change from baseline of fibrinogen during 24 weeks from treatment onset
- Change from baseline of fibrinogen during 76 weeks from treatment onset
- Change from baseline of D-dimer during 24 weeks from treatment onset
- Change from baseline of D-dimer during 76 weeks from treatment onset

Protocol
 Trial ID: NN7415-4255
 UTN: U1111-1179-3872
 EudraCT no.: 2016-000614-29

~~CONFIDENTIAL~~

Date: 28 December 2017
 Version: 4.0
 Status: Final
 Page: 27 of 124

Novo Nordisk

- Change from baseline of prothrombin fragment 1 + 2 (F1 + 2) during 24 weeks from treatment onset
- Change from baseline of F1 + 2 during 76 weeks from treatment onset
- Change from baseline of prothrombin time (PT) during 24 weeks from treatment onset
- Change from baseline of PT during 76 weeks from treatment onset
- Change from baseline of activated partial thromboplastin time (APTT) during 24 weeks from treatment onset
- Change from baseline of APTT during 76 weeks from treatment onset
- Change from baseline of antithrombin (AT) during 24 weeks from treatment onset
- Change from baseline of AT 76 weeks from treatment onset
-

Supportive secondary pharmacokinetic endpoints

- Concentration of concizumab prior to the last dose administration at 24 weeks
- Concentration of concizumab prior to the last dose administration at 76 weeks

Supportive secondary pharmacodynamic endpoints

Plasma free TFPI concentration

- Value prior to the last dose administration at 24 weeks
- Value prior to the last dose administration at 76 weeks

Thrombin generation

- Peak thrombin generation (nM) prior to the last dose administration at 24 weeks
- Peak thrombin generation (nM) prior to the last dose administration at 76 weeks

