8.1.11 Follow-up Part

8.1.11.1 Visit 17 (End of trial)

Visit 17 is to be scheduled on trial day 589 (84 weeks) with a visit window of minus 7 days

Assessments are to be performed according to [Table 2–1](#) and the assessment results from concomitant medication, physical examination, body measurements (weight only), vital signs and details of adverse events must be entered into the eCRF.

Investigator is to perform compliance check of treatment and reporting of bleeding episodes through reviewing collected data from the eDiary. Patients must be asked if their female partner has become pregnant during the trial (see Section [12.5.1](#)).

Protocol
 Trial ID:NN7415-4255
 UTN:U1111-1179-3872
 EudraCT no.:2016-000614-29

~~CONFIDENTIAL~~

Date:	28 December 2017	Novo Nordisk
Version:	4.0	
Status:	Final	
Page:	52 of 124	

The patient will be asked to return all used, partly used and unused turoctocog alfa (rFVIII), eDiary device and Trial card. Drug accountability must be performed for turoctocog alfa (rFVIII) including injection kits, if applicable. Unused sodium chloride syringes should be returned to site at every visit and new sodium chloride syringes should be dispensed to the patient.

End of trial information must be entered in the End of Trial form in the eCRF.

End of trial Call must be made in the IWRS.

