8.5.2.7 Anti-concizumab antibodies

Sampling will be performed at all visits except at visit 3. Samples will be collected pre-dose at visit 2, 9 and 16.

Assessment of binding antibodies against concizumab (anti-drug antibodies (ADA)) will be performed at specialised laboratories whereas assessment of neutralising antibodies will be performed at Novo Nordisk A/S.

Analysis for ADA will be done as listed in [Table 2-1](#), with a bridging ECL assay (binding ADA assay), using labelled concizumab for antibody capture and detection. If a sample is confirmed positive in the confirmatory assay, the sample is considered antibody positive. Confirmed positive samples will be characterised for binding to IgG backbone, CDR region or the S241P mutation. Furthermore, positive samples will be characterised for neutralising activity using a modified TFPI functionality assay (neutralising ADA assay). All antibody assays are validated according to international guidelines and recommendations.

The following analyses will be available:

Protocol
 Trial ID:NN7415-4255
 UTN:U1111-1179-3872
 EudraCT no.:2016-000614-29

~~CONFIDENTIAL~~

Date:	28 December 2017	Novo Nordisk
Version:	4.0	
Status:	Final	
Page:	67 of 124	

- Anti-concizumab antibody assay
- Specificity assay (Anti-concizumab antibodies cross reacting with IgG4 backbone, CDR region or S241P mutation)
- Anti-concizumab neutralising antibody assay

Samples will be drawn at all visits except at visit 3. The samples will be analysed in batches during the trial and results will be available to the data monitoring committee approximately every third month after the first patient has been dosed (Section [12](#)). Neutralising antibodies will be analysed and reported at the end of trial. A detailed description of the assay methods will be included in the antibody analysis report at the end of the trial.

Investigators will be notified in case their patient is shown to have developed neutralising antibodies against concizumab.

Samples for the determination of anti-drug antibodies collected during the treatment period must be drawn prior to administering trial products.

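### The 76-week antibody endpoint leaves a completer's visit 17 sample (week 84) out of every stated antibody endpoint and summary, and the 76-week TEAE label does not match the TEAE definition

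*Protocol*

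**What the plan says.** Safety and immunogenicity are secondary objectives (Protocol 4.1.2). The long-term antibody endpoint is "Occurrence of anti-concizumab antibodies during 76 weeks from treatment onset" (4.2.2.1, in both version 3 and version 4.0). Section 17.6.2 then fixes the reporting: "Frequency of binding anti-concizumab antibodies will be listed and summarised by time frame according to the two endpoint definitions". The two definitions are the windows of at least 24 weeks and of 76 weeks. The text after 4.2.3.3 places all 76-week endpoints in the extension part, whereas 8.1 places visit 17 in a separate follow-up part.

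On sampling, 8.5.2.7 says: "Sampling will be performed at all visits except at visit 3". Visit 16, the last day of treatment, is on day 533, week 76, with a window of 7 days either way (8.1.10.3). For the end of trial, 8.1.11.1 says: "Visit 17 is to be scheduled on trial day 589 (84 weeks) with a visit window of minus 7 days". A patient who stops early has visit 17 eight weeks after his last dose (8.1.4). Under 8.5.2.7, measurable binding antibodies at the end-of-trial visit lead to additional visits for up to one year.

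For adverse events, 17.6.2 lists "Number of TEAEs during 76 weeks from treatment onset" as an endpoint, and in the same section a TEAE "is defined as an event that has onset from the first exposure to treatment until the last visit in the trial". Adverse events are collected through visit 17 (12.2).

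Section 17 is visible only in version 3 (18 December 2017). The version 4.0 text shown ends before its section 17, but it repeats the 76-week endpoints and the visit 17 schedule.

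**The concern.** The follow-up part exists to observe patients after concizumab stops, and the protocol treats an end-of-trial antibody result as important enough to trigger further visits. Yet a completer who is first positive at that visit is not a case under the long-term endpoint and appears in no stated antibody frequency. The same follow-up sample does count for a patient who stopped early enough. One proportion would therefore combine patients with and without a post-treatment sample, and the excluded ones are the majority.

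For adverse events the trouble is smaller. By definition an event with onset in week 80 is a TEAE, but the endpoint label stops at week 76. Two analysts working from this text could report different long-term TEAE counts.

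**Working it through.** **Inputs.** Visit 2 is trial day 1 (8.1.9.1). Visit 16: day 533, week 76. Visit 17: day 589, week 84, minus 7 days. Antibody sampling: every visit except visit 3. Started on treatment: 33; planned completers: 30 (6.1).

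**1. Reproduce the visit days.** Day = 7 × week + 1.
- Week 76: 7 × 76 + 1 = 533, as stated.
- Week 84: 7 × 84 + 1 = 589, as stated.
- Total duration: 2 + 76 + 8 = 86 weeks, as stated.

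**2. Can a completer's visit 17 fall inside 76 weeks?** Its window is day 589 − 7 = 582 to day 589, that is weeks 83 to 84. With visits on schedule, the earliest date is 582 − 533 = 49 days past the cut and the latest is 589 − 533 = 56 days. So it cannot.

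**3. What is left out.**
- Scheduled antibody samples after the first dose: visits 4 to 17, 14 in all. Visits 4 to 16 (13) are nominally inside the window and visit 17 (1) is outside.
- Post-baseline time outside the 76-week label: 8/84 = 9.5% per completer.

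**4. Who keeps the follow-up sample?** Visit 17 is at last dose + 8 weeks. It falls at or before week 76 if the last dose is at or before week 76 − 8 = 68, or week 76 − 7 = 69 if the minus-7-day window is used. Planned non-completers number 33 − 30 = 3, and only those stopping by then qualify. The exclusion applies to the 30 planned completers.

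**5. Direction.** For a count of patients ever positive, removing one sampling occasion cannot add a case. It lowers the count or leaves it unchanged.

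**6. Size, illustration only.** The documents give no rate of antibodies first appearing after treatment.
- Exact (Clopper-Pearson) two-sided 95% upper limit for 0/33: 1 − 0.025^(1/33) = 10.6%.
- For 1/33 = 3.0%, the upper limit solves (1 − p)^33 + 33p(1 − p)^32 = 0.025, giving p = 15.8%.
- If a fraction p of 30 completers were first positive at visit 17, the chance that the endpoint misses at least one is 1 − (1 − p)^30. This is 26% at p = 1%, 60% at 3%, 79% at 5% and 96% at 10%.

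**7. TEAE wording side by side.** The definition runs from first exposure to the last visit, which is week 84 for a completer. The endpoint label runs to week 76. An event with onset between the two is treatment-emergent and is listed, but is outside the labelled count.

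**The case against.** The case for leaving this alone has several parts.

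*A 76-week endpoint matches the 76-week treatment period and is defensible for a supportive phase 2 endpoint.* As an on-treatment summary this stands. It does not explain why follow-up samples of early discontinuers fall inside the window, or why no stated summary covers those of completers.

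*The visit 17 result is not lost.* This is true. A reader might infer that late antibodies go undetected or unmanaged. The documents do not support that: the sample is analysed, a positive result leads to further visits, and end-of-trial data of patients who withdraw are retained and used (18.3). What is missing is a place in an endpoint or frequency summary.

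*Visit 17 is not the only sample taken off concizumab.* Correct. Visit 1 and the pre-dose sample at visit 2 are also off drug, and antibody-positive patients may give later samples. Visit 17 is the only scheduled sample after treatment stops.

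*Drug masking is not shown.* A reader might infer that all on-treatment samples are unreliable, because the bridging assay uses labelled concizumab for capture and detection (8.5.2.7). The protocol gives no drug-tolerance limit and says the assays are validated. Masking is therefore an assumption, and no amount of bias can be claimed from it. No anti-concizumab antibodies had been seen in earlier trials (18.1), so late cases may be rare.

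*The TEAE definition and the TEAE endpoint do different jobs.* The definition says which events qualify and the endpoint says over what period they are counted; the same definition serves the 24-week endpoint too. This has force. A reader might infer that TEAE reporting stops at week 76. It does not, since events are collected to visit 17 and all are listed. A mismatch of wording remains.

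*Section 17 of version 4.0 is not visible, and separate table rows are usually left to the SAP.* Both are fair as limits on certainty. The 76-week window itself is stated in version 4.0, section 4.2.2.1.

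**Conclusion.** The point holds for immunogenicity in this limited form: as written, a completer's only scheduled post-treatment antibody sample is in no stated endpoint or summary, while that of a patient whose last dose is at or before about week 68 is included. The effect on the ever-positive count is nil or downward. Its size cannot be determined from the protocol; the shift from 0/33 to 1/33 shows only what a single such case would do. For TEAEs the finding is a mismatch between label and definition that affects the count for weeks 76 to 84, not a loss of data.

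This rests on visits taking place on schedule, on reading the 76-week window literally, and on version 4.0 keeping the summary rule seen in section 17.6.2 of version 3. It should be corrected, but it does not touch the primary analysis.

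**What to change.** In sections 4.2.2.1 and 17.6.2, define the long-term antibody and TEAE endpoints as running from first dose to visit 17, that is week 84 for completers or eight weeks after the last dose for those who stop early. This also brings the TEAE endpoint into line with its definition. Report the on-treatment period and the follow-up period as separate rows, so that the on-treatment figure remains available and follow-up is handled alike for completers and discontinuers.

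The cost is a wording change and one extra table row, with no new samples or visits. The stated incidences may come out slightly higher.

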17.6.3 Supportive secondary pharmacokinetic endpoints

- Concentration of concizumab prior to the last dose administration at 24 weeks.
- Concentration of concizumab prior to the last dose administration at 76 weeks.

The pharmacokinetic endpoints will be summarised and listed.

Protocol
Trial ID:NN7415-4255
UTN:U1111-1179-3872
EudraCT no.:2016-000614-29

~~CONFIDENTIAL~~

Date: 18 December 2017
Version: 3
Status: Final
Page: 104 of 124

Novo Nordisk

17.6.4 Supportive secondary pharmacodynamic endpoints

Free TFPI concentration:

- Value prior to the last dose administration at 24 weeks.
- Value prior to the last dose administration at 76 weeks.

Thrombin generation:

- Peak thrombin generation (nM) prior to the last dose administration at 24 weeks.
- Peak thrombin generation (nM) prior to the last dose administration at 76 weeks.
- Endogenous thrombin potential (nM*min) prior to the last dose administration at 24 weeks.
- Endogenous thrombin potential (nM*min) prior to the last dose administration at 76 weeks.
- Velocity index (nM/min) prior to the last dose administration at 24 weeks.
- Velocity index (nM/min) prior to the last dose administration at 76 weeks.

The PD endpoints will be summarized and listed.

17.7 Exploratory endpoints

17.7.1 Exploratory safety endpoints

- Number of adverse events related to technical complaints during at least 24 weeks from treatment onset
- Number of adverse events related to technical complaints during at least 76 weeks from treatment onset

Adverse events related to technical complaints will be listed and summarised.

17.7.2 Exploratory patient reported outcome endpoints

- Change in Hemo-TEM after 24 weeks from treatment onset
- Change in Hemo-TEM after 76 weeks from treatment onset
- Change in SF-36v2 after 24 weeks from treatment onset
- Change in SF-36v2 after 76 weeks from treatment onset

Protocol
 Trial ID:NN7415-4255
 UTN:U1111-1179-3872
 EudraCT no.:2016-000614-29

~~CONFIDENTIAL~~

Date:
 Version:
 Status:
 Page:

18 December 2017
 3
 Final
 105 of 124

Novo Nordisk

- Change in SDS after 24 weeks from treatment onset
- Change in SDS after 76 weeks from treatment onset
- Change in TSQM after 24 weeks from treatment onset
- Change in TSQM after 76 weeks from treatment onset
- Change in SIAQ-ISRQ after 24 weeks from treatment onset
- Change in SIAQ-ISRQ after 76 weeks from treatment onset
- Status of PGI-C after 24 weeks from treatment onset
-
- Change in H-DAT after 76 weeks from treatment onset
-

Patient reported outcomes (PROs) will be collected using questionnaires at visits 1, 2, 4, 5, 6, 7, 8, 9, 10 and 16.

Patient reported outcome questionnaires to be analysed:

- Haemophilia Treatment Experience Measure (Hemo-TEM)
- Validated Hemophilia Regimen Treatment Adherence Scale – Prophylaxis (VERITAS-Pro[®]) or Validated Hemophilia Regimen Treatment Scale (/ VERITAS-PRN[®])¹⁴
- 36-Item Short Form Health Survey (SF-36v2) (4 week recall)¹⁵
- Patient Global Impression of Change (PGI-C)
- Sheehan Disability Scale (SDS)¹⁶
- Treatment Satisfaction Questionnaire for Medication (TSQM, version II)¹⁷⁻¹⁹
- Haemophilia - Device Assessment Tool (H-DAT)
- Injection Site Reaction Questionnaire (ISRQ) domain of SIAQ (SIAQ-ISRQ)²⁰

VERITAS-Pro[®] or VERITAS-PRN[®], SF-36v2, SDS, TSQM, H-DAT and SIAQ-ISRQ will be scored according to their respective scoring algorithms. Change from visit 2 to visit 9 and change from visit 2 to visit 16 will be described.

Protocol
 Trial ID: NN7415-4255
 UTN: U1111-1179-3872
 EudraCT no.: 2016-000614-29

~~CONFIDENTIAL~~

Date: 18 December 2017
 Version: 3
 Status: Final
 Page: 106 of 124

Novo Nordisk

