8.6 Other assessments

8.6.1 Patient reported outcomes

In this trial a newly developed disease specific PRO - the Hemophilia Treatment Experience Measure (Hemo-TEM) - is being validated. In order to assess the psychometric properties of Hemo-TEM, other questionnaires will be provided; see further [appendix 1](#).

The following ePRO questionnaires are used:

- Haemophilia Treatment Experience Measure (Hemo-TEM)
- Validated Hemophilia Regimen Treatment Adherence Scale – Prophylaxis (VERITAS-Pro®)/Validated Hemophilia Regimen Treatment Scale (/ VERITAS-PRN®)¹⁴
- 36-Item Short Form Health Survey (SF-36v2) (4 week recall)¹⁵
- Patient Global Impression of Change (PGI-C)
- Sheehan Disability Scale (SDS)¹⁶
- Treatment Satisfaction Questionnaire for Medication (TSQM, version II)¹⁷⁻¹⁹
- Haemophilia - Device Assessment Tool (H-DAT)

Protocol
 Trial ID:NN7415-4255
 UTN:U1111-1179-3872
 EudraCT no.:2016-000614-29

~~CONFIDENTIAL~~

Date: 18 December 2017
 Version: 3
 Status: Final
 Page: 70 of 124

Novo Nordisk

- Injection Site Reaction Questionnaire (ISRQ) domain of SIAQ (SIAQ-ISRQ)²⁰

The PROs should be assessed at the scheduled visits following the order listed below:

- visit 1 (Hemo-TEM, VERITAS-Pro[®] or VERITAS-PRN[®])
- visit 2 (Hemo-TEM, SF-36v2, SDS, TSQM, SIAQ-ISRQ)
- visit 4 (PGI-C, Hemo-TEM)^a
- visit 5 (PGI-C, Hemo-TEM)
- visit 6 (PGI-C, Hemo-TEM)
- visit 7 (PGI-C, Hemo-TEM)
- visit 8 (PGI-C, Hemo-TEM)
- visit 9 (PGI-C, Hemo-TEM, SF-36v2, SDS, TSQM, H-DAT, SIAQ-ISRQ)
- visit 10 (Hemo-TEM, SF-36v2, SDS, TSQM, SIAQ-ISRQ)
- visit 16 (Hemo-TEM, SF-36v2, SDS, TSQM, H-DAT, SIAQ-ISRQ)

At visit 1 before any visit-related activities all patients should complete Hemo-TEM and VERITAS-Pro[®] (if the patient at baseline receives prophylactic treatment) / VERITAS-PRN[®] (if patient at baseline receives on demand treatment).

At visit 2 before any visit-related activities all patients should complete Hemo-TEM, SF36v2, SDS, TSQM and SIAQ-ISRQ.

At visit 4-8: before any visit-related activities the patient should complete the PGI-C before the Hemo-TEM. These are the rules that apply:

- If the patient responds “1” to question 1 in the PGI-C, the patient should also complete the Hemo-TEM. In this case the patient should not fill in the PGI-C any more in the trial and the Hemo-TEM only again at visit 9.

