4.2.3.2 Exploratory patient-reported outcome endpoints

- Change in Hemo-TEM after 24 weeks from treatment onset
- Change in Hemo-TEM after 76 weeks from treatment onset
- Change in SF-36v2 after 24 weeks from treatment onset
- Change in SF-36v2 after 76 weeks from treatment onset
- Change in SDS after 24 weeks from treatment onset
- Change in SDS after 76 weeks from treatment onset
- Change in TSQM after 24 weeks from treatment onset
- Change in TSQM after 76 weeks from treatment onset
- Change in SIAQ-ISRQ after 24 weeks from treatment onset
- Change in SIAQ-ISRQ after 76 weeks from treatment onset
- Status of PGI-C after 24 weeks from treatment onset
- Change in H-DAT after 76 weeks from treatment onset

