8.6 Other assessments

8.6.1 Patient reported outcomes

In this trial a newly developed disease specific PRO - the Hemophilia Treatment Experience Measure (Hemo-TEM) - is being validated. In order to assess the psychometric properties of Hemo-TEM, other questionnaires will be provided; see further [appendix 1](#).

The following ePRO questionnaires are used:

- Haemophilia Treatment Experience Measure (Hemo-TEM)
- Validated Hemophilia Regimen Treatment Adherence Scale – Prophylaxis (VERITAS-Pro®)/Validated Hemophilia Regimen Treatment Scale (/ VERITAS-PRN®)¹⁴
- 36-Item Short Form Health Survey (SF-36v2) (4 week recall)¹⁵
- Patient Global Impression of Change (PGI-C)
- Sheehan Disability Scale (SDS)¹⁶
- Treatment Satisfaction Questionnaire for Medication (TSQM, version II)¹⁷⁻¹⁹
- Haemophilia - Device Assessment Tool (H-DAT)

Protocol
 Trial ID:NN7415-4255
 UTN:U1111-1179-3872
 EudraCT no.:2016-000614-29

~~CONFIDENTIAL~~

Date: 28 December 2017
 Version: 4.0
 Status: Final
 Page: 70 of 124

Novo Nordisk

- Injection Site Reaction Questionnaire (ISRQ) domain of SIAQ (SIAQ-ISRQ)²⁰

The PROs should be assessed at the scheduled visits following the order listed below:

- visit 1 (Hemo-TEM, VERITAS-Pro[®] or VERITAS-PRN[®])
- visit 2 (Hemo-TEM, SF-36v2, SDS, TSQM, SIAQ-ISRQ)
- visit 4 (PGI-C, Hemo-TEM)^a
- visit 5 (PGI-C, Hemo-TEM)
- visit 6 (PGI-C, Hemo-TEM)
- visit 7 (PGI-C, Hemo-TEM)
- visit 8 (PGI-C, Hemo-TEM)
- visit 9 (PGI-C, Hemo-TEM, SF-36v2, SDS, TSQM, H-DAT, SIAQ-ISRQ)
- visit 10 (Hemo-TEM, SF-36v2, SDS, TSQM, SIAQ-ISRQ)
- visit 16 (Hemo-TEM, SF-36v2, SDS, TSQM, H-DAT, SIAQ-ISRQ)

At visit 1 before any visit-related activities all patients should complete Hemo-TEM and VERITAS-Pro[®] (if the patient at baseline receives prophylactic treatment) / VERITAS-PRN[®] (if patient at baseline receives on demand treatment).

At visit 2 before any visit-related activities all patients should complete Hemo-TEM, SF36v2, SDS, TSQM and SIAQ-ISRQ.

At visit 4-8: before any visit-related activities the patient should complete the PGI-C before the Hemo-TEM. These are the rules that apply:

- If the patient responds “1” to question 1 in the PGI-C, the patient should also complete the Hemo-TEM. In this case the patient should not fill in the PGI-C any more in the trial and the Hemo-TEM only again at visit 9.

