- If the patient responds “0” or “2” to question 1 in the PGI-C, the patient should not complete any other questionnaires at this visit, but should repeat the procedure at next visit.

At visit 9 if the patient has responded “0” or “2” in the PGIC at all previous visits, the patient should complete PGI-C. All patients should complete Hemo-TEM, SF-36v2, SDS, TSQM, H-DAT and SIAQ-ISRQ.

At visit 10 all patients should complete Hemo-TEM, SF-36v2, SDS, TSQM and SIAQ-ISRQ.

At visit 16 all patients should complete Hemo-TEM, SF-36v2, SDS, TSQM, H-DAT and SIAQ-ISRQ. The investigator must check the ePROs for potential AEs and SAEs.

The completed ePROs should be transmitted to the ePRO database by the investigator at each visit.

All PROs can be found in [Appendix I](#).

Protocol
Trial ID:NN7415-4255
UTN:U1111-1179-3872
EudraCT no.:2016-000614-29

~~CONFIDENTIAL~~

Date: 28 December 2017
Version: 4.0
Status: Final
Page: 71 of 124

Novo Nordisk

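### H-DAT and VERITAS have no visit 2 score to measure change from, and week-24 PGI-C status is collected only from patients who never answered 1 earlier

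*Protocol*

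**What the plan says.** Section 17.7.2 (version 3) lists the patient-reported endpoints, including "Change in H-DAT after 76 weeks from treatment onset" and the PGI-C endpoint, which section 4.2.3.2 words identically: "Status of PGI-C after 24 weeks from treatment onset". A scoring sentence follows. It names VERITAS-Pro or VERITAS-PRN, SF-36v2, SDS and TSQM, and ends "H-DAT and SIAQ-ISRQ will be scored according to their respective scoring algorithms". The next sentence sets the analysis: "Change from visit 2 to visit 9 and change from visit 2 to visit 16 will be described".

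Section 8.6.1 fixes what is collected. VERITAS appears once, at the screening visit: "visit 1 (Hemo-TEM, VERITAS-Pro[®] or VERITAS-PRN". The visit 2 battery is "visit 2 (Hemo-TEM, SF-36v2, SDS, TSQM, SIAQ-ISRQ", with neither H-DAT nor VERITAS. H-DAT appears at visits 9 and 16.

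PGI-C starts at visit 4 and is gated. Of a patient who answers 1 to its first question at any of visits 4 to 8, section 8.6.1 says: "In this case the patient should not fill in the PGI-C any more in the trial". At visit 9 the instruction covers only patients who answered 0 or 2 "in the PGIC at all previous visits, the patient should complete PGI-C".

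Version 4.0 keeps the same endpoints (4.2.3.2) and the same schedule and gate (8.6.1). The supplied text of version 4.0 stops at section 12.5.1, so its section 17.7.2 cannot be seen.

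**The concern.** The analysis section and the collection schedule of the same protocol do not fit together in two ways.

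First, read literally, the change rule asks for differences from a visit at which two of the six named instruments are not administered. For H-DAT this affects a listed endpoint. For VERITAS it affects only the analysis sentence.

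Second, the PGI-C endpoint is a status at week 24, but whether a patient has a week-24 value depends on that patient's own earlier answers. A summary of the visit 9 responses would describe the patients who never gave a particular answer, while carrying a label that suggests the whole trial population.

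At stake is whether these exploratory results can be produced and read as labelled. A statistical analysis plan can redefine an endpoint, but it cannot recover an H-DAT baseline or a visit 9 PGI-C that was never collected.

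**Working it through.** The plan states no numerical result for this point, so the check sets section 17.7.2 against section 8.6.1, instrument by instrument.

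| Instrument | Visits with data (8.6.1) | Visit 2 to 9 | Visit 2 to 16 |
|---|---|---|---|
| SF-36v2, SDS, TSQM, SIAQ-ISRQ | 2, 9, 10, 16 | yes | yes |
| H-DAT | 9, 16 | no | no |
| VERITAS | 1 | no | no |

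**H-DAT.** Both planned differences need a visit 2 value, and none exists. The only change the schedule supports is from visit 9 to visit 16. That change starts after 24 weeks of treatment and is not the one section 17.7.2 defines.

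**VERITAS.** With a single assessment at visit 1, no change from any baseline is possible.

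**PGI-C.** Visit 9 is week 24 (section 8.1.9.5, trial day 169). The gate works as follows:

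- Answer of 1 at any of visits 4, 5, 6, 7 or 8: no further PGI-C, so no visit 9 value.
- Answer of 0 or 2 at all five visits: PGI-C completed at visit 9.

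A visit 9 value is therefore absent by design for every patient with an earlier 1. No rule in the protocol says how that earlier 1 enters the week-24 status.

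How many patients this removes depends on a rate the documents do not give. As an illustration only, assume a constant chance p of answering 1 at each of the five visits, independent between visits. The share without a visit 9 PGI-C is then 1 − (1 − p)^5, applied here to the 33 patients planned to start treatment:

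- p = 0.05: 1 − 0.95^5 = 0.226, or 7.5 of 33
- p = 0.10: 1 − 0.90^5 = 0.410, or 13.5 of 33
- p = 0.20: 1 − 0.80^5 = 0.672, or 22.2 of 33
- p = 0.30: 1 − 0.70^5 = 0.832, or 27.5 of 33

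The illustration shows that the missing share could be anywhere from modest to most of the trial. It does not estimate the share.

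**The case against.** The strongest reply is that little is lost.

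- **VERITAS.** No change in VERITAS is listed as an endpoint in 4.2.3.2 or 17.7.2, and the change sentence names no instrument. It can be read as meant for those with change endpoints. This stands as far as endpoints go: a reader might infer that three planned endpoints are lost, and the documents do not support that. The sentence still follows directly on a list that includes VERITAS and needs correcting.
- **H-DAT.** The protocol lists only a 76-week change, with no 24-week one, which fits a first assessment at visit 9. A visit 9 to 16 change is available from scheduled data. That stands too, so H-DAT does not come back empty. What fails is the stated visit 2 baseline.
- **PGI-C.** Patients who answered 1 do have a recorded response, and a statistical analysis plan, not available here, could say how to use it. The gate also looks deliberate: section 8.6.1 says the other questionnaires serve the validation of Hemo-TEM, and a 1 triggers Hemo-TEM completion. This is fair. A reader might infer that the endpoint will overstate or understate perceived change, but the meanings of 0, 1 and 2 are in Appendix I, which is not shown, so the direction cannot be determined. The selection of the visit 9 sample is nevertheless certain.
- **Sections 8.1.9.5 and 8.6.1.** Section 8.1.9.5 lists PGI-C at visit 9 without a condition, and a reader might infer a contradiction. There is none, because 8.1.9.5 says the questionnaires are completed according to 8.6.1. The visit list in 8.6.1 is likewise unconditional, with the rules set out after it.
- **Version.** The change sentence is visible only in version 3. The H-DAT and PGI-C endpoints, the schedule and the gate are confirmed in version 4.0.

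**Conclusion.** The point holds, at minor severity. As defined in section 17.7.2 of version 3, change from visit 2 cannot be computed for H-DAT or VERITAS in any patient. The one listed endpoint affected is the 76-week change in H-DAT, which has no visit 2 or pre-treatment baseline in either version. PGI-C status at week 24 is observed only in patients with no answer of 1 at visits 4 to 8. The resulting selection follows from the gate alone; the size and direction of any bias cannot be determined from the documents.

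These conclusions rest on the section 8.6.1 schedule being followed as written and, for the visit 2 baseline, on version 4.0 not having changed section 17.7.2. Every endpoint concerned is exploratory. The proof-of-concept criteria rest on the annualised bleeding rate and are untouched.

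**What to change.** 1. **H-DAT:** define the endpoint as the level at visits 9 and 16, with change from visit 9 to visit 16, in sections 4.2.3.2 and 17.7.2. Wording only.
2. **VERITAS:** take it out of the change sentence in section 17.7.2 and report it as a visit 1 descriptor. Wording only.
3. **PGI-C:** choose one of two routes.
   - Have all patients complete it at visit 9 by amending the visit 9 rule in section 8.6.1, and keep the gate at visits 4 to 8 for timing the Hemo-TEM. The cost is one short questionnaire at an existing visit for some patients. On the planned dates (first treatment 30 August 2017; trial day 169 is 168 days later, 14 February 2018), the first visit 9 fell after version 4.0 of 28 December 2017, so this was still possible at that amendment.
   - Redefine the endpoint as first or any answer of 1 by week 24. This needs no new data.
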